ALSPAC has an effective an efficient team of professional service staff who will integrate with the leads for this specific research. A *Senior Management Team* is responsible for day to day activity required to deliver ALSPAC objectives. Information concerning the job of running ALSPAC and this

work flows from this group to the *ALSPAC Executive* weekly. The ALSPAC Executive is effectively held to account by the *ALSPAC Board* and questions regarding governance, science or strategy can be referred to one or more of the ALSPAC Board, The *Independent Scientific Advisory Board* or the Scientific Director.

Figure 1. ALSPAC management structure

The structure of ALSPAC management has been set up to specifically enable clear and effective flow of information from the operating ALSPAC teams (clinic/data/linkage/lab/operation and administration) through the Senior Management Team (SMT) to the ALSPAC Executive.

Aims and Objectives

Our objective is to coordinate the collection of epidemiological-grade biological test data using (home-based serological testing kits) for COVID-19 infection across a series of select studies across the UK. This aims to complement existing studies based on COVID-19 serology and provide information on prevalence across 4 main axes of variation important for developing mitigation strategy relevant evidence (age, geography, socio-economic position, ethnicity/ancestry) and with the ability to assess this against information on existing co-morbidities.

In ALSPAC specifically we will **firstly** address prevalence across those of differing age range in the South West of the UK. We now know (UKBiobank preliminary data – **Figure 1**) that there is likely to be both a detectable number and age gradient of infection exposure in the South West (reflecting a broader trend in the UK) and would be able to provide an important estimate in our sample of parents and "children of the 90s" participants.

Secondly, we will assess the extent of disparity between symptoms and infection (i.e. the importance of covariables/morbidities for the presentation of events). Through our COVID-19 questionnaires (https://wellcomeopenresearch.org/articles/5-127,

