Participants meeting the Eligibility Criteria described above will be invited to take part via email (See Appendix I). The initial invite provides information about the study and ask them to consent online if they wish to take part. (see Data Collection – Consent section for further details on the consent process).

If a response is not received with ~3 days a reminder email will be sent (See Appendix I).

A timeline, included the recruitment phase, is shown in Appendix II.

Sample Size

Based on the inclusion criteria above, there are 5,830 participants who responded Yes to follow-up (G0 – 3254, G1 – 2493, G1 partners - 83 G1 partners)

Plus, an additional 1345 participants who completed the first COVID-19 questionnaire but not the second.

Study power

Throughout the planning of this work we have worked with [name] (who has also advised the REACT team) with respect to the assessment of whether the sampling frame we can provide is viable for our analytical questions (objectives). Is it clear that the linkage of data from regional and national cohorts represents, in combination with results from other current or prospective national-level COVID-19 studies, presents an opportunity to conduct a wide range of analyses covering various aspects of COVID-19 epidemiology. Relevant to ALSPAC, however, the assessment of the performance of data collected is can be presented in terms of a single sample being able to recruit 4-5000 participants (based on deploying 5000 home kits to those consented from a pool of more than 7000 COVID-19 questionnaire completers).

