If, after reading the documents, participants wish to take part they are directed to an online consent form (See Appendix I) hosted on REDCap (https://projectredcap.org/). There are several declarations to ensure that they have read and understood the study documentation and what is required of them.

At this stage we are also collecting address details to ensure that we can deliver the kits to the correct address.

Note: the following question will be added to the consent form to screen out participants with coagulation disorders (unable to update the attachment in Appendix I at this time)

"Do you have an increased risk of bleeding (for example taking blood thinners such as Warfarin, or any medical condition that would mean a self-delivered finger prick with a lancet would not be advisable)?

- 1. Yes
- 2. No
- 3. Don't know

If answer is Yes participant will receive the following message.

We cannot send you an antibody test, as there are risks associated with this test for people who have an increased risk of bleeding. Thank you for your interest."

Mailing of antibody kits

Following confirmation of consent participants address will be securely transferred to a third-party printing/mailing house (covered by a Data Processing Agreement). The antibody testing kits, instruction booklet and cover letter (See Appendix I for full documents) will be collated and set out as per the timeline in Appendix II.

If test results are not uploaded within ~3 days a reminder email will be sent (See Appendix I)

Taking the test

Participants are supplied with full instruction to complete a COVID-19 home antibody test (See Appendix I).

The kit (assembled by Una Health) consists of:

- One Orientgene test cassette in foil pouch (pouch contains test cassette and small pipette)
- One 1mL dropper bottle of buffer
- One Owen Mumford Unistik touch lancet, 23g, 2mm, yellow
- One Owen Mumford Unistik touch lancet, 21g, 2m, orange
- One sterile wipe
- One sterile cotton wool ball
- One small plaster.

In summary particpants will use the lancet to obtain a drop of blood. The blood is applied to the test cassettee and buffer is added. Once developed, 10-15 min, lines indicated the test results. These are

described in the instruction leaflet. Particpants are insturcted to take a photo of the test result to submit online

Questionnaire and submitting results

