The cover letter and reminder email will contain details of the online form for submitting test results (See Appendix 1) hosted on REDCap (https://projectredcap.org/). Participants are first presented with a brief set of questions on symptom history and previous tests they may have completed. The is followed by questions on completion of the COVID-19 home antibody test, any problems encountered and asking them to report the results against a list of possible results.

We are also asking participants to upload a photo of the test result to allow for validation of the interpretation of the result. Submitting this photo is optional.

Lastly there is a section on complete the study, this includes submitting their Date of Birth, the opportunity to submit a free text comment and opt out of a Prize Draw.

Compensation

There are no individual level incentive/compensation vouchers for this study. Participants completing before the deadline will be entered into prize draw to win one of 3 £100 vouchers.

Safety and Safeguarding

Some ALSPAC participants have additional requirements or specific circumstances that require us to take a more personalised or sensitive approach. These participants are identified within our contact management system – termed safeguarding. This system enables us to shield them from inappropriate contact and to provide them with the support necessary to continue to play an active part in the study. For example, requirement for large print questionnaire, access requirements to attend a clinic. Safeguarded participants will be reviewed on a case by case basis by the participation team and a decision taken on whether it is appropriate to include them.

Adverse Events

University of Bristol has registered this study with the Yellow Card scheme. Contact details for the ALSPAC (Children of the 90s) team is included in all study documentation to participants. If a participant reports any adverse events to us via phone/email these will be reported to MHRA via the Yellow Card scheme either by ALSPAC study staff and/or we will give the participant details to report themselves via https://yellowcard.mhra.gov.uk/. Manufacturer (Fortress Diagnostics Ltd) will be informed of any device specific AEs.

Data Management

Online data collection will be managed by ALSPAC data team staff on University of Bristol servers.

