To access the online data collection each participant has a unique security token in addition to a username/password. The link emailed to the participant contains their specific security token. When the participant clicks on the link, it maps the security token to the participant and logs them in. This allows access to the questionnaire and for data to be submitted. This has worked well for several years and mechanisms have been built in to minimise the risk of someone other than the participant getting hold of their details.

Each section has its own submit button, once each one has been clicked own the relevant section is completed and cannot be accessed again. Participants cannot go back to sections once they have been completed (and submitted); this reduces the risk associated with someone else being able to access the online data collection (i.e. if an email was shared/hacked and the unique linked obtained),

if someone else did access it they would not find any information only blank sections of the form. The following statement is included "Once you have clicked 'Submit' you will not be able to return to that section or edit your answers."

The consent data will be collected separately to the COVID-19 Home antibody test questionnaire under a different identifier. The consent form asks for the participants' address to send the COVID-19 Home antibody test to. The address information will be regularly exported and deleted from the server. The address data will be compared to the administrative address on file and updated where the participant has requested this. The addresses will be stored in a secure file area accessible to only a subset of ALSPAC staff. The addresses will be encrypted and shared securely with Gemini West who will be mailing the test kits to participants.

The questionnaire that participants are asked to complete asks for the participant to upload an image of their test result. A script will strip the images of any additional information (metadata) that they main contain (such as location data) to leave just the image itself.

All data collected will be deposited in the ALSPAC data repository and data access requests will be processed via the ALSPAC executive Committee, as per the ALSPAC Access Policy.

Analysis Plan

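### New symptom-history items are collected on the result-submission form with no requirement to answer before reading the cassette, so analyses that use them are open to result-aware recall

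*Protocol*

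**What the plan says.** Under Questionnaire and submitting results, the protocol describes the route to the form: "The cover letter and reminder email will contain details of the online form for submitting test results". On that form, "Participants are first presented with a brief set of questions on symptom history and previous tests they may have completed"; questions on doing the test and on its result follow.

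Under Taking the test, which comes before the form is described, the participant reads the device: "Once developed, 10-15 min, lines indicated the test results". The next step is a photograph: "Particpants are insturcted to take a photo of the test result to submit online". Under Mailing of antibody kits, the reminder is triggered by results not having been uploaded.

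Under Data Management, "Each section has its own submit button", and a submitted section cannot be reopened. The same section calls the new form a questionnaire and says that consent data are held apart from it under a different identifier.

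Under Aims and Objectives, the second objective is stated as "we will assess the extent of disparity between symptoms and infection". It is introduced through the existing COVID-19 questionnaires, whose self-reported symptoms run from October 2019. The Analysis Plan speaks of association with questionnaire symptom report, and of probabilistic case assignment from questionnaire, health-record and serological data, without saying which questionnaire is meant.

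**The concern.** Symptom history is most useful as evidence against serology when the person giving it does not know the serology. Here the participant is the reader of the test, and the form is presented as the place to upload what was read. Someone who has just seen a positive result may reclassify an old cough as COVID-19; someone who has seen a negative may leave it out. That error is differential by test result. It pushes the symptom-serostatus association upward and the apparent asymptomatic share of positives downward, and those are the quantities behind a comparison of symptoms with infection. In the case-assignment work there is a further cost: if symptom reports have been shaped by the serology, the two are no longer separate pieces of evidence, and their agreement is overstated.

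**Working it through.** **Order of events.** The protocol gives no figure on this point, so there is nothing to reproduce. Set side by side, the sections give this sequence: the kit arrives with a cover letter giving the form details; the test is done, read and photographed; the form is opened; symptoms are asked first; the result is reported. Putting symptoms first on screen does not hide a result that has already been read. The section lock stops later editing, but it protects the symptom answers only if that section is submitted before reading. No sentence in the protocol requires this.

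**Which analyses are exposed.**
- Symptoms in the period covered by earlier questionnaires: a pre-test report exists, because every invitee completed at least one. Analyses using only these reports are not exposed.
- Symptoms since the last questionnaire: the new form is the only self-report described. Under Sample Size, the protocol lists 5,830 who agreed to follow-up, then: "Plus, an additional 1345 participants who completed the first COVID-19 questionnaire but not the second". For these people the gap runs from their first questionnaire. They are 1345 / (5830 + 1345) = 1345 / 7175 = 18.7% of invitees. Their share of those tested is not known.
- Symptom association and case assignment under the Analysis Plan: exposed if the new form counts as questionnaire data.

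**Illustrative size for an analysis resting wholly on the new items.**

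Inputs from Study power: N = 5000 (upper end of 4000 to 5000) and prevalence 5%, giving 250 positives and 4750 negatives. Assumed, with no source in the document: 20% of negatives truly have symptoms; the true rate p in positives is 20%, 40% or 60%; a share u of symptom-free positives newly report symptoms; a share d of symptomatic negatives drop theirs.

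Observed rates: positives p + (1 − p)u; negatives 0.20(1 − d). Odds ratio (OR) = odds in positives / odds in negatives.

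Worked case, p = 0.40, u = 0.10, d = 0.05:
- positives 0.40 + 0.60 × 0.10 = 0.46; negatives 0.20 × 0.95 = 0.19
- OR = (0.46/0.54) / (0.19/0.81) = 3.63, against a true (0.40/0.60) / (0.20/0.80) = 2.67
- standard error (SE) of log OR = √(1/115 + 1/135 + 1/902.5 + 1/3847.5) = 0.132
- bias = ln(3.63/2.67) / 0.132 ≈ 2.3 SE

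| True OR | u 5%, d 2% | u 10%, d 5% | u 20%, d 10% |
|---|---|---|---|
| 1.00 (p = 20%) | 1.30 | 1.66 | 2.56 |
| 2.67 (p = 40%) | 3.09 | 3.63 | 4.94 |
| 6.00 (p = 60%) | 6.69 | 7.58 | 9.68 |

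In the middle row the bias is 1.1, 2.3 and 4.7 SE, and the apparent asymptomatic share of positives falls from 60% to 57%, 54% and 48%. With u = d = 0, as for reports made before the result is known, this bias is zero. If only some participants answer after reading, u and d shrink in proportion.

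**The case against.** The strongest reply is that the second objective is built on the earlier questionnaires, which predate this test. That stands. A reader might infer that the objective as a whole is biased; the Aims and Objectives section does not support this, because recall on the new form cannot alter reports already on file.

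A reader might also infer that the 1345 have no result-free symptom data, or that no later analysis could undo the problem. Neither holds. Those people completed the first questionnaire. Analysts can restrict to earlier reports or, for the period already covered, compare earlier and new reports within person by serostatus. Only symptoms since the last questionnaire lack that check.

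It is fair, too, that knowledge of the result is inferred. The form details come with the kit, so a participant could submit the symptom section first. The instruction booklet, cover letter and questionnaire are listed in Appendix I but not reproduced, and they may already set the order.

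Finally, the choice of primary symptom source could be left to a statistical analysis plan. That answers the wording of the Analysis Plan but not the order of collection, which no analysis document can restore once the cassette has been read. Earlier reports are not perfectly result-free either, since some participants may have had another test before.

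**Conclusion.** The point holds in a limited form and is of moderate severity. The new symptom and previous-test items are open to result-aware recall because the protocol text does not require them before the cassette is read. The effect reaches only analyses that use those items: the symptom association and case assignment if the new form is included, and symptoms arising since each person's last questionnaire. The direction follows if positives tend to reinterpret past symptoms and negatives to discount them. The size cannot be had from the document; the figures above depend on assumed symptom rates and recall shifts and show only that modest shifts could exceed sampling error in some scenarios. The conclusion would weaken if the unseen participant materials already ask for the symptom section first.

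**What to change.** In Taking the test and in Questionnaire and submitting results, instruct participants to complete and submit the symptom and previous-test section before opening the test pouch. Use the existing section lock and record a time stamp for each section. Add one line to the cover letter and one to the instruction booklet. No item needs rewording, so only the timing differs from any questions shared with REACT.

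The time stamps give a partial check: since the test takes 10-15 minutes to develop, a gap of under 10 minutes between the symptom section and the result section shows that the test had been started first. A longer gap does not prove the right order.

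In the Analysis Plan, state that pre-result symptom reports (earlier questionnaires, plus new items submitted before testing) are primary for the second objective and for case assignment, and that post-result reports serve only in sensitivity analysis.

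Moving the items to the consent stage is not recommended, because consent data sit under a different identifier and would have to be linked.

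The cost is one extra step before the test, small edits to two participant documents and the form set-up. Some participants may still not follow the order.

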Appendix

I. Draft documents

| Title | Full text | Adapted from REACT study? |
|-----------------------------|--------------------------------|-------------------------------|
| 1. Email Invite v0.1 | | No |
| | 1. Email Invite | |
| | v0.1.docx | |
| 2. B3566_PIS_v0.1 | | Yes |
| | | Track changes showing update |
| | B3566_PIS_v1.1_upd | from Protocol v1.0 documents. |
| | ates.doc | |
| | | |
| | B3566_PIS_v1.1_upd | |
| | ates_dean.doc | |
| 3. Instruction Booklet | PDF | Yes |
| | Bristol Orientgene | |
| | Antibody Instruction \ | |
| 4. Instructional Video v1.0 | | Yes |
| | 4. Instructional Video | |
| | v1.0.docx | |
| 5. Email Reminder v0.1 | W | No |
| | 5. Email Reminder | |
| | v0.1.docx | |
| 6. Consent Form | PDF | No |
| | Covid_Antibody_Con sent.pdf | |
| | Plus additional screening | |
| | question related to | |
| | coagulation disorders will be | |
| | included. | |
| 7. Cover Letter | | No |
| | 7. Cover Letter | |
| | v0.1.docx | |

| 8. Email Test Reminder | | No |
|------------------------------|-----------------------|----------------------------|
| | 8. Email Test | |
| | Reminder v0.1.docx | |
| 9. Questionnaire and Results | PDF | Q7-13 – use in REACT study |
| | Covid_Antibody_Que | |
| | stionnaire.pdf | |
| | PDF | |
| | Covid_Antibody_Ima | |
| | ge_Upload.pdf | |
| | PDF | |
| | Covid_Antibody_Com | |
| | pleting_Questionnaire | |

II. Timeline

Timeline below is based on an anticipated start date of 20 July 2020.

Green boxes are contact points with participants
